### 10.11. Randomization (4 Week Follow-Up)

Subjects will be assigned to a group at random during the randomization visit. Randomization will occur at 4 weeks.

Subjects will be randomized in a 2:1 ratio to the Elevated Night Pacing ON or to the Elevated Night Pacing OFF group.

Sites will receive this randomization assignment from the randomization schedule, which is automatically populated on the eCRF.

Procedures to be performed and data to be collected at Randomization include:

- Physical Assessment (including weight, heart rate, symptoms, and blood pressure)
- Medications
- NYHA Class
- MN Living with Heart Failure Questionnaire
- 6 Minute Walk Test
- Echo\*
- Blood Draw\*\*
- Randomization assignment
- Device Interrogation/ (initial)
- Save-to-Media (initial)
- Device Programming, see Table 7: Programming Recommendations at 4 Week Follow-Up
- Device Interrogation (final) - this needs to be completed at the end of the visit after programming has been completed
- Save-to-Media (final)
- Adverse Events (report new/assess ongoing AEs), Study Deviations, System Modifications, Device Deficiencies, Crossovers (as they occur)

\*The echo must be sent to the Echo Core Laboratory for analysis, with a copy of the echo remaining at the site. Details of the Echo Core Laboratory, type of echo to be performed, and the review process will be provided in an Echocardiography Handbook (provided under separate cover).

\*\* The blood sample must be sent to the Blood Core Laboratory for analysis. Details of the blood core lab and the blood draw process will be provided under separate cover.

For any subject who has an abnormal NT-proBNP, troponin or LVEF measurement as defined in the Safety Assessment (Section 10.19. Assessment of Safety) and the investigator elects to discontinue elevated night pacing, a subsequent visit will be necessary for the elevated night pacing to be programmed OFF if the subject was randomized to the elevated pacing ON arm. The subject should continue to be followed through the 12 week visit.

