**Table 9: Risks Related to Elevated Pacing**

Risk	Potential Patient Harm	Mitigation
Pacing at a sustained elevated rate that causes symptoms during the day or night	Increased risk of Dizziness, palpitations, heart racing, shortness of breath, difficulty sleeping	
At the time of enrollment, subjects will be evaluated to whether they can tolerate a pacing rate of 100bpm
 
Subjects will be instructed to call study team if they are experiencing symptoms
 
Symptoms will be gathered from subjects using phone calls following enrollment, 4 week, and 8 week clinic visits
 
A programming checklist will be used at enrollment, 4 week, 8 week, and Exit visits to ensure appropriate programming of the Sleep Function parameters

Pacing at a sustained elevated rate may initiate or make heart failure or AF or ischemia worse	Increased risk of chest pain, atrial arrhythmia, or ischemia	We are monitoring troponin and NT-proBNP levels for worsening heart failure and troponin for ischemia. If levels worsen the subject will have their elevated pacing therapy programmed Off
Mode-switch during atrial arrhythmia results in a higher ventricular non-tracking pacing rate because the lower rate is programmed to 100bpm	Increased risk of Dizziness, palpitations, heart racing, shortness of breath	Symptoms will be gathered from subjects using phone calls following enrollment, 4 week, and 8 week clinic visits

Pacing at a sustained elevated rate that causes symptoms following unscheduled clinic visits. (Any minor telemetry activation, such as reprogramming, magnet application, or CareLink transmission will suspend the Sleep Function and the pacer will start pacing at the programmed Lower Rate.)
	
Increased risk of Dizziness, palpitations, heart racing, shortness of breath
	
Subjects will be instructed to call study team if they are experiencing symptoms
 
Subjects will also be asked their heart rate, which the subject can read using a finger pulse oximeter monitor that will be given to them at Baseline to use
 
Centers will be trained to instruct subjects to come to center for unscheduled visits

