##### Analysis Methods

The proportion of subjects who remain in the study up until the 4 week visit without exiting due to intolerable symptoms, increase in NT-proBNP levels, decrease in LVEF or increase in troponin will be calculated along with the lower bound of the one-sided 95% confidence interval

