##### Analysis Methods

The proportion of subjects who remain in the study from the 4 week visit to the 8 week visit without exiting due to intolerable symptoms, increase in NT-proBNP levels, decrease in LVEF or increase in troponin will be calculated along with the lower bound of the one-sided 95% confidence interval for both arms (elevated night pacing left ON versus elevated night pacing programmed OFF).

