##### Analysis Methods

The proportion of subjects who remain in the study up until the 4 week visit without exiting due to intolerable symptoms, increase in NT-proBNP levels, decrease in LVEF or increase in troponin will be calculated along with the lower bound of the one-sided 95% confidence interval.

As the REVAMP study was designed to explore the feasibility of the study therapy, there was no pre-specified threshold for overall safety and tolerability. In order to provide the most conservative estimate of the safety and tolerability, any study exit prior to the 4 week visit will be assumed to be related to intolerable symptoms or safety issue. Also, study

deaths attributed by the investigative site as related or unknown relative to the study therapy prior to the 4 week visit will be counted against the proportion of subjects remaining in the study. A variable active4wk will be set to equal 1 for subjects who remain in the study up until the 4 week visit and will be set to equal 0 otherwise. The proportion of subjects remaining in the study, along with the lower bound of the one-sided 95% confidence interval can be found using code similar to:

```
PROC FREQ DATA=Revamp_Test;
  TABLE active4wk / BINOMIAL(EXACT LEVEL='1') ALPHA=0.1;
RUN;
```

As this study is exploring the feasibility of the study therapy, sensitivity analysis may be performed, exploring various assumptions regarding ambiguous study exits.

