##### Analysis Methods

The proportion of subjects who remain in the study from the 4 week visit to the 8 week visit without exiting due to intolerable symptoms, increase in NT-proBNP levels, decrease in LVEF or increase in troponin will be calculated along with the lower bound of the one-sided 95% confidence interval for both arms (elevated night pacing left ON versus elevated night pacing programmed OFF).

This analysis will be similar to the 4 week safety and tolerability endpoint, using a variable active8wk to indicate whether a subject remains in the study up until the 8 week visit. The same conservative approach to study exits and death used for the 4 week time point will be implemented for the 8 week time point. The proportion of subjects remaining in the study,

along with the lower bound of the one-sided 95% confidence interval can be found using code similar to:

```
PROC FREQ;
  TABLE active8wk / BINOMIAL(EXACT LEVEL='1') ALPHA=0.1;
RUN;
```

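### Elevated pacing stopped for safety after week 4 is coded as tolerated at week 8, because the endpoint counts only study exit or death as failure

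*SAP*

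**What the plan says.** **Endpoint.** CIP 14.1.1 defines tolerability in each period as the proportion remaining in the study "without exiting due to intolerable symptoms, increase in NT-proBNP levels, decrease in LVEF or increase in troponin". SAP 7.9.1 turns this into two indicators. For week 4: "A variable active4wk will be set to equal 1 for subjects who remain in the study up until the 4 week visit". For week 8 it proposes "using a variable active8wk to indicate whether a subject remains in the study up until the 8 week visit". Any exit counts as failure, as do deaths judged related or of unknown relation. The stated motive is: "In order to provide the most conservative estimate of the safety and tolerability". An optional sensitivity analysis is described as "exploring various assumptions regarding ambiguous study exits".

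**Stopping pacing for marker results.** CIP 10.11 covers the subject with an abnormal NT-proBNP, troponin or LVEF whose investigator chooses to discontinue. If that subject was randomised to ON, pacing is switched off at a later visit, and then: "The subject should continue to be followed through the 12 week visit". CIP Table 9 gives the mitigation for worsening troponin or NT-proBNP as: "If levels worsen the subject will have their elevated pacing therapy programmed Off". It does not mention exit. CIP 10.19 leaves withdrawal to the investigator's discretion, and 10.15.4 discourages withdrawal by investigators.

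**Stopping pacing for symptoms.** CIP 10.19 permits pacing to be switched off when reprogramming does not resolve intolerable symptoms. CIP 10.15 lists essentially the same situation among the reasons for which subjects are exited.

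**The concern.** The quantity of interest is whether patients can continue elevated night pacing safely. The indicators measure whether patients stay in the study. The CIP separates the two, sensibly, by following subjects after pacing is stopped. A subject taken off therapy because troponin rose or LVEF fell can therefore be reported as having tolerated it.

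The marker route is the clear case because it needs no departure from the plan. The three markers are named in the endpoint as reasons for failure, yet the procedure prescribed when one of them prompts discontinuation keeps the subject in the study. Those components register only if an investigator also withdraws the subject.

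At stake is the week 8 ON proportion, which CIP section 14 presents as evidence on longer-term safety and tolerability. It would be too favourable by an amount that the planned output does not reveal.

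**Working it through.** **Step 1: trace one subject through the coding.** The subject is randomised to ON, and the week 4 results then lead the investigator to discontinue.

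1. Table 4 of the CIP schedules blood and echo at Baseline, week 4, week 8 and week 12. The first scheduled post-baseline markers are therefore drawn at the week 4 visit.
2. The subject reached that visit, so active4wk = 1.
3. The subject completed 4 weeks of pacing, so belongs to the week 8 analysis set.
4. Pacing is switched off at a later visit and follow-up continues under 10.11, so active8wk = 1.
5. There is no exit and no death, so neither the conservative rule nor the optional sensitivity analysis touches the record.

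The result is a success at both time points.

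**Step 2: the week 4 symptom route.** If 10.15 is followed, the subject exits and active4wk = 0, which is correct. If a site uses only the permission in 10.19 and retains the subject, active4wk = 1. SAP 7.9.1 then leaves that subject out of the week 8 set as unable to tolerate treatment, so the failure appears in neither endpoint. This depends on site practice.

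**Step 3: size.** The plan states no expected proportion or threshold to reproduce. Its code uses an exact binomial interval with ALPHA=0.1, which gives 0.1/2 = 0.05 in each tail, matching the stated one-sided 95% bound. For x successes in n, the bound is the 5th percentile of Beta(x, n − x + 1); for x = n this equals 0.05^(1/n).

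Inputs:
- About 30 subjects paced (CIP 7, SAP 6) and 2:1 allocation, so ON is 30 × 2/3 = 20.
- If 3 of 30 are lost before week 4, ON is 27 × 2/3 = 18.
- The number of retained stops is assumed. No other exits, unless stated.

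| Retained stops in ON | n = 20, as coded | n = 20, stops counted | n = 18, as coded | n = 18, stops counted |
|---|---|---|---|---|
| 1 | 100% (86.1%) | 95.0% (78.4%) | 100% (84.7%) | 94.4% (76.2%) |
| 2 | 100% (86.1%) | 90.0% (71.7%) | 100% (84.7%) | 88.9% (69.0%) |
| 3 | 100% (86.1%) | 85.0% (65.6%) | 100% (84.7%) | 83.3% (62.3%) |

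Lower bounds are in brackets. At n = 20, each retained stop adds 5 points to the reported proportion; three raise the bound by 86.1 − 65.6 = 20.5 points.

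Other exits do not close the gap. With 1 exit and 3 retained stops at n = 20, the plan reports 19/20 = 95.0% (78.4%), while 16/20 = 80.0% (59.9%) stayed on pacing.

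For week 4, and only if step 2's retention occurs, one such subject in 30 changes 96.7% (85.1%) to 100% (90.5%).

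**The case against.** **Week 4 is largely protected.** A reader might infer that both endpoints are affected alike, and so that the 4-week figure, which helps decide whether to pursue the therapy, is overstated. The documents do not support that. Stops prompted by scheduled marker results come too late for week 4, and 10.15 calls for exit in the symptom case. Only the looser wording of 10.19 leaves a gap. The preference in 10.15.4 for keeping subjects in the study applies to those already randomised. This objection stands.

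**OFF subjects have no pacing to stop.** Putting pacing stops into the ON versus OFF comparison would add a failure that one arm cannot have. Stops prompted by week 4 results also reflect the first 4 weeks rather than the additional 4 being compared. This stands too, and it shapes the fix.

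**The endpoint is openly a retention measure and the study is exploratory.** It is ancillary and has no threshold, so no formal decision reverses. Marker changes are analysed in SAP 7.9.2, adverse events in 7.9.3, and crossovers are recorded. All true, but the proportion is reported under a safety and tolerability label, and none of those analyses corrects it.

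**Counting every exit as failure is already conservative.** That rule pulls the estimate down for other subjects. It does not recode the retained ones.

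**Conclusion.** The point holds for week 8. When 10.11 is followed as written, pacing stopped for abnormal week 4 markers is coded a success at both time points, against the SAP's aim of a conservative estimate. For week 4 the gap is conditional on a site switching pacing off for symptoms without the exit in 10.15.

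The coding error runs one way: counting a retained stop as failure can only lower the reported proportion. Its size in this trial is unknown, because the documents give no stop rate. The figures above illustrate assumed counts of 1 to 3 in an ON arm of 18 or 20, and are not estimates of bias. Nor do they show that the ON versus OFF retention comparison is itself wrong. As a comparison of who stays in the study, it remains valid.

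**What to change.** 1. **Recode.** In CIP 14.1.1 and SAP 7.9.1, define failure as elevated night pacing stopped for symptoms or safety in the period, or exit or death as now. Derive it from the crossover records and device interrogations already collected. For stops before randomisation, check that a crossover record is made; the week 4 interrogation is the backstop.
2. **Week 8 reporting.** Present the recoded figure as the proportion tolerating continued pacing in the ON arm, with its exact lower bound, and show stops triggered by week 4 results as a separate line. Keep the exit-based proportion for ON versus OFF.
3. **Reconcile 10.15 with 10.19.** State one rule for intolerable symptoms that reprogramming does not relieve. Under the recoding, exit and retention both give a failure, so the result no longer turns on site habit.

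**Cost.** The recoding needs wording and programming, with no new measurements. The case report forms are not in the documents, so the crossover form may need a reason field. Revised CIP text needs IRB approval at each site (CIP 16.5). If item 3 is settled in favour of retention, symptom stops will attend scheduled visits they would otherwise miss; settling it as exit avoids that. The reported tolerability may also be less favourable.

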#### Determination of Subjects for Analysis

All enrolled subjects that are programmed with elevated night pacing.

#### **Safety and Tolerability – 8 weeks**

##### Hypothesis

Following a 4 week period of elevated night pacing, compare the safety and tolerability of subjects in the ON and OFF arm for an additional 4 weeks of elevated night pacing

##### Analysis Methods

The proportion of subjects who remain in the study from the 4 week visit to the 8 week visit without exiting due to intolerable symptoms, increase in NT-proBNP levels, decrease in LVEF or increase in troponin will be calculated along with the lower bound of the one-sided 95% confidence interval for both arms (elevated night pacing left ON versus elevated night pacing programmed OFF).

This analysis will be similar to the 4 week safety and tolerability endpoint, using a variable active8wk to indicate whether a subject remains in the study up until the 8 week visit. The same conservative approach to study exits and death used for the 4 week time point will be implemented for the 8 week time point. The proportion of subjects remaining in the study,

along with the lower bound of the one-sided 95% confidence interval can be found using code similar to:

```
PROC FREQ;
  TABLE active8wk / BINOMIAL(EXACT LEVEL='1') ALPHA=0.1;
RUN;
```

### Determination of Subjects for Analysis

All subjects that completed 4 weeks of elevated night pacing. Subjects that were unable to tolerate or withdrew from the treatment during the first 4 weeks because of safety or other issues will not be included in this analysis.

#### 7.9.2. Ancillary Safety Endpoint – NT-proBNP, troponin, LVEF

##### **NT-proBNP, troponin, LVEF – 4 weeks**

###### Hypothesis

For each of the main safety measures (NT-proBNP, troponin and LVEF), comparisons will be done to see if there are changes from baseline after a 4 week period of elevated night pacing.

###### Analysis Methods

A paired comparison of the value at the end of the period compared to the value at the start of the period will be calculated. A two-sided paired t-test will be performed testing the hypothesis

$$H_0: \mu = 0$$

$$H_a: \mu \neq 0$$

Where  $\mu$  = difference in measurement from baseline to week 4 visit

SAS code similar to the following will be used to evaluate the 4 week ancillary safety endpoints:

```
PROC TTEST;
  PAIRED ntprobp0*ntprobp4;
RUN;

PROC TTEST;
```

```
PAIRED troponin0*troponin4;  
RUN;  
  
PROC TTEST;  
  PAIRED lvef0*lvef4;  
RUN;
```

By default, subjects that do not have 4 week measurements available will be excluded from the analysis.

#### Determination of Subjects for Analysis

All subjects that completed 4 weeks of elevated night pacing. Subjects that were unable to tolerate or withdrew from the treatment during the first 4 weeks because of safety or other issues will not be included in this efficacy analysis.

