### 10.13. **Unscheduled Follow-Up Visits**

An unscheduled visit is defined as any unplanned visit by the subject to the study site. Routine visits or other planned visits are not collected.

The following information is recommended to be collected at an unscheduled follow-up visit at the discretion of the investigator if deemed necessary:

- Physical Assessment (including weight, heart rate, symptoms and blood pressure)
- Medication changes
- Echo\*
- Blood draw\*\*
- Device Interrogation (initial)
- Save-to-Media (initial)
- Program the Sleep Function and parameters to protocol
- Device Interrogation (final) - this needs to be completed at the end of the visit after programming has been completed
- Save to Media (final)

The following is required:

- Adverse Events (report new/assess ongoing AEs)
- Study Deviations
- System Modifications
- Device Deficiencies
- Crossovers

\*The echo must be sent to the Echo Core Laboratory for analysis, with a copy of the echo remaining at the site. Details of the Echo Core Laboratory, type of echo to be performed, and the review process will be provided in an Echocardiography Handbook (provided under separate cover).

\*\* The blood sample must be sent to the Blood Core Laboratory for analysis. Details of the blood core lab and the blood draw process will be provided under separate cover.

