### **10.19. Assessment of Safety**

As a feasibility study, the primary objective is to assess the feasibility of using elevated night pacing as a therapy for heart failure with preserved ejection fraction. This includes assessing the safety and tolerability of elevated night pacing, as described in Section 5.1. Background. Subjects who experience intolerable symptoms from the elevated pacing therapy and whose symptoms cannot be reconciled by reprogramming may have the elevated night pacing programmed OFF. NT-proBNP, troponin, assessed from peripheral blood samples and LVEF, as assessed by the echo, will be collected at Baseline and at the 4 week visit. Subjects with increases in NT-proBNP and troponin from Baseline to the 4 week visit should be monitored by the investigator for accompanying symptoms, including worsening heart failure and cardiac ischemia. Symptoms should be reported as adverse events and subjects will be considered for withdrawal from the study, at the discretion of the investigator. Subjects with 4 week LVEF < 45% whose baseline LVEF was at least 55% may also be considered for withdrawal from the study at the discretion of the investigator. NT-proBNP, troponin and LVEF will be further assessed as discussed in Section 10.11. Randomization (4 Week Follow-Up) and Section 14.1.2. Ancillary Safety Endpoint – NT-proBNP, troponin, LVEF. Further information on the collection of Adverse Events is discussed in Section 12.5. Reporting of Adverse Events.

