## Determination of Subjects for Analysis

All adverse events reported for subjects actively receiving elevated night pacing will be included.

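### The 4-week NT-proBNP, troponin and LVEF safety tests leave out subjects who stopped pacing for safety or intolerance, so they can understate harm, and SAP 7.9.1 only partly makes up for it

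*SAP*

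**What the plan says.** SAP 7.9.2 presents these as safety variables: "For each of the main safety measures (NT-proBNP, troponin and LVEF), comparisons will be done to see if there are changes from baseline" after 4 weeks of pacing. The method is a paired comparison: "A two-sided paired t-test will be performed testing the hypothesis" of zero mean change.

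Two separate rules then restrict who is analysed.

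- The Analysis Methods text deals with missing values: "By default, subjects that do not have 4 week measurements available will be excluded from the analysis".
- The Determination of Subjects text keeps only those who completed 4 weeks of pacing. It adds that subjects who were "unable to tolerate or withdrew from the treatment during the first 4 weeks because of safety or other issues will not be included". The sentence ends by labelling the test as efficacy: those who stopped "because of safety or other issues will not be included in this efficacy analysis". Protocol 14.1.2 has the same rule and the same label. The same exclusion appears under the 4-week efficacy endpoints, for example MNLWHF and 6 Minute Walk in SAP 7.9.4 and 7.9.5.

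For the 4-week adverse event summary, SAP 7.9.3 says: "All adverse events reported for subjects actively receiving elevated night pacing will be included".

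Protocol 10.19 provides for stopping pacing without mentioning study exit. Subjects "whose symptoms cannot be reconciled by reprogramming may have the elevated night pacing programmed OFF". Protocol 10.15, however, lists intolerable symptoms that reprogramming cannot relieve among the reasons for leaving the study.

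**The concern.** Under this rule, entry to a safety test depends on a safety outcome. The subjects removed are those in whom a biomarker rise or an LVEF fall is most plausible, and the rule removes them even when a week-4 value exists. Subjects without a value are already handled by the missing-data sentence, so the population rule has an effect of its own only on subjects who were measured.

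No sensitivity analysis is specified for this test, whereas the 6 Minute Walk endpoint has one. SAP section 6 says that the 4-week safety and tolerability objective will help decide whether the therapy goes forward. A supporting biomarker result that looks flat because stoppers were left out could therefore carry weight in that decision.

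**Working it through.** **Step 1. Follow one subject through the plan.** Take a subject who starts pacing, has it programmed OFF in week 2 for symptoms, stays in the study, and attends week 4.

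- Data available: protocol Table 4 schedules a blood draw and an echo at week 4 for subjects still in the study. Both are also "recommended to be collected at an unscheduled follow-up visit at the discretion of the investigator if deemed necessary". A week-4 value can therefore exist.
- SAP 7.9.2: excluded, because 4 weeks of pacing were not completed.
- SAP 7.9.1: `active4wk` is 1 for a subject who remains in the study to week 4. It does not ask whether pacing is still ON, so this subject is a success.
- SAP 7.9.3: the event that prompted the switch-off began under pacing and is counted. A later event is counted or not depending on whether the sentence defines a group of subjects or a time window. The 4-week text does not say. The 8-week text does use an on-pacing window for the ON arm, which makes the time-window reading likely.

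**Step 2. Size for the paired tests.** The documents give no SD, effect size, stopping rate or alpha for these tests, so there is no plan figure to reproduce. All inputs except the sample size are assumptions.

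- n = 30 treated (SAP section 6)
- SD of change = 1; completers' mean change = 0
- k = 3 to 5 stoppers, all measured, with mean shift d = 1.5 to 2 SD retained in full
- two-sided 5% paired t-test

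All-treated mean change = k × d / 30. Rejection rates are from 40,000 simulated trials.

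| k | d (SD) | All-treated mean (SD) | Rejection, all treated | Rejection, completers |
|---|---|---|---|---|
| 3 | 1.5 | 3 × 1.5 / 30 = 0.15 | 9.1% | about 5% |
| 3 | 2 | 3 × 2 / 30 = 0.20 | 11.1% | about 5% |
| 5 | 1.5 | 5 × 1.5 / 30 = 0.25 | 17.8% | about 5% |
| 5 | 2 | 5 × 2 / 30 = 0.33 | 24.6% | about 5% |

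The completer mean is 0 in every row. If half of each shift had reversed by week 4, the all-treated means would halve, to 0.15 / 2 = 0.075 and 0.33 / 2 = 0.17 SD at the two ends.

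**Step 3. Size for SAP 7.9.1.** The code asks for an exact interval with ALPHA=0.1, which does give the stated one-sided 95% lower bound (0.1 / 2 = 0.05). With 30 treated and no study exits, but k subjects off pacing before week 4:

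| k | Planned definition (in study) | In study and on pacing |
|---|---|---|
| 3 | 30/30, lower bound 90.5% | 27/30 = 90.0%, lower bound 76.1% |
| 5 | 30/30, lower bound 90.5% | 25/30 = 83.3%, lower bound 68.1% |

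**The case against.** The strongest reply is that SAP 7.9.1 is where stopping is meant to be counted. It covers every subject programmed with the therapy and treats any study exit before week 4 as intolerance or a safety issue. That stands for exits. It does not reach a subject who stops pacing and stays.

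Other points limit the concern, and they stand.

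- Few values may be affected. The schedule has no blood draw or echo at Early Study Exit, so most early exits have nothing to add.
- A subject taken off pacing because of abnormal week-4 results (protocol 10.11) has already completed the 4 weeks and stays in the 4-week test.
- Measurements before week 4 are only unscheduled and discretionary. Most earlier stops would therefore be for symptoms, and the documents say nothing about the biomarker change in those subjects.
- The hypothesis concerns change after 4 weeks of pacing, so a completer analysis answers a legitimate question. Protocol 5.1 and 7.2 report that in animals the dilation diminishes or reverses once pacing stops. A value taken after switch-off may have partly recovered and could pull the mean towards zero.

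A reader might infer that harm is removed from the safety results as a whole, or that the 8-week tests share the defect for later stoppers. The documents do not support either. Study exits count as failures in 7.9.1. Protocol 12.1 collects all SAEs and all system-, programming- and cardiovascular-related events throughout. The 8-week tests call for the value at time of exit from subjects who leave between weeks 4 and 8. A reader might also take it as settled that the 4-week summary discards events after switch-off. That is a likely reading, but the text does not state it.

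**Conclusion.** The point holds for the 4-week NT-proBNP, troponin and LVEF tests. The exclusion is explicit, it is the same in protocol and SAP, it is mislabelled as efficacy, and it selects on the outcome under study. These tests can understate harm, mainly through subjects who stop pacing before week 4, remain in the study and are measured. SAP 7.9.1 offsets this only in part, because it measures retention in the study and not continuation of pacing. The 4-week adverse event wording is ambiguous and needs settling.

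The illustrated size is an all-treated mean of +0.15 to +0.33 SD, with rejection of about 9% to 25% against about 5% for completers. It rests entirely on assumed stopping numbers and shifts, on every stopper having a week-4 value, and on no reversal after pacing stops. The true effect could be smaller, and it is nil if nobody stops and stays. In an unpowered feasibility study this is a correction the plan should make, not a fatal flaw.

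**What to change.** 1. **SAP 7.9.2 and protocol 14.1.2, 4 weeks.** Analyse every subject programmed with elevated night pacing who has a baseline and a week-4 value, whether or not pacing is still ON. Report the completer analysis beside it. Use the last unscheduled value only as a sensitivity analysis, because that sampling is discretionary. Delete the word efficacy.
2. **SAP 7.9.3 and protocol 14.1.3, 4 weeks.** Report all adverse events from first programming to the week-4 visit, each flagged as on or after therapy.
3. **SAP 7.9.1.** Keep `active4wk`, and also report the proportion still in the study and still on pacing at week 4, with the same exact lower bound.
4. **Protocol 10.15 and 10.19.** Reconcile the two passages on intolerable symptoms (study exit in one, pacing programmed OFF in the other), since the answer decides how many subjects stop and stay.

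The cost is wording in both documents and a few extra table rows, with no new procedures. The downside is that values taken after pacing stops may have partly reversed and can dilute the mean. That is why both analyses should be shown.
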